3.2 Primary Study Endpoints

Neurological:

- Change from baseline score using Friedreich's Ataxia Rating Scale (FARS Assessment) tool at 12 and 24 weeks.
- Changes in spinal cord fractional anisotropy, based on axial DTI measurements prescribed at the C1, T1, and L1 levels at 24 weeks.

Cardiac:

- Changes in Cardiac MRI from baseline to 12 and 24 weeks:
 - Left ventricular structural and functional characteristics (systolic function by ejection fraction and systolic strain, diastolic function, LV mass to determine ventricular hypertrophy and degree of heart failure, myocardial fibrosis by late gadolinium enhancement).
- Changes in Echocardiogram from baseline to 24 weeks:
 - Left ventricular mass, volumes, systolic and diastolic function, and strain.
- Changes in Electrocardiogram from baseline to 24 weeks to assess for electrophysiological improvement of the myocardium.
- Changes in biomarkers for heart failure and hypertrophy (ST2, BNP, Cardiac Troponin) from baseline, at 12 weeks and 24 weeks.

3.3 Secondary Study Endpoints

- Changes in spinal cord and cerebellum volume by MRI from baseline to 24 weeks after initiation of therapy:
 - Spinal cord and cerebellar volumes based on high-resolution 3D volumetric T1- and T2-weighted datasets.

- Metabolic change from baseline at 12 weeks and 24 weeks measured by:
 - Glucose tolerance test, fasting blood glucose and hemoglobin A1C at baseline, 12 (+/-), and 24 (+/-) weeks to assess for improvement of diabetes mellitus.
- Change in mitochondrial biomarkers from baseline to 24 weeks:
 - Assess for upregulation of relevant mitochondrial proteins (frataxin and ETC complexes I-IV) and (ii) reduction of urine F2-isoprostane as a measure of oxidative stress.

3.4 Exploratory Endpoints

- Change in cardiac stress-regadenoson and Blood Oxygenation Level Dependent (BOLD) MRI from baseline at 12 and 24 weeks after treatment:
 - Myocardial oxygenation by BOLD sequence on 3T MRI
 - Myocardial perfusion index via cardiac stress-regadenoson MRI from baseline to 24 weeks
- Change in cerebellar metabolites (Cho, Cr, NAA), based on 3D MRS data obtained over the posterior fossa and upper cervical cord.
- Change in follistatin and myostatin levels from baseline at 3 (+/-1), and 24 (+/-1) weeks as a measure of muscle improvement.

3.5 Primary Safety Endpoints

Safety endpoints will include:

- Distribute a diary to each study participant in order to date and record symptoms of adverse events along with drug intake. All participants will be asked to contact study coordinator or PI via phone in the case of an adverse event, which will then be documented in the source documents. Participants will be asked to bring the diary along with their drug bottles to each clinic visit.
- Comparison between treatment groups of the incidence and types of reported adverse events including increase in migraine headaches, bruising or bleeding.

The consumption of cocoa products containing the epicatechins has been reported to be associated with increased likelihood of migraine development [37]. However, the migraine effect has not been validated in subsequent clinical trials, and, if it exists, has been attributed to the presence of phenylethylamine [38].

Anti-clotting like effects have been described for foods containing members of the flavonoid family including epicatechin, such as cocoa, tea, and guarana. There is no report as to the effects that epicatechin per se may have on phenomena such as platelet aggregation or clotting times [14, 38, 39].

The modest effects on platelet aggregation of food containing polyphenols has been cited as one basis for beneficial cardiovascular effects. To our knowledge, no adverse

event involving platelet inhibition has been described in any study of foods or their extracts of cocoa, guarana, or tea. Nonetheless, we deemed it prudent to exclude patients with thrombocytopenia or clotting disorders.

- Potential risk based on the biological activities of (+)-epicatechin includes hypotension through presumed mechanism of nitric oxide (NO) mediated vasodilation [40]. Of note is the fact that so far, no blood pressure reducing effects by (-)-epicatechin have been reported in normotensive subjects. With cocoa based studies, blood pressure reducing effects are only reported in humans that have high blood pressure [41]. In the study by Ottaviani et al., the vasodilating effects of (+)-epicatechin in humans were only 25% of those of (-)-epicatechin when given at the same doses (1.5 mg/kg) [21]. There is the possibility that patients undergoing pharmacologic treatment for high blood pressure if given epicatechin may develop hypotension through additive or synergistic effects.
- Guarana effects on toxic and behavioral parameters were assessed in rats and mice subsequent to acute and chronic administrations. Experimental parameters included tests for antioxidant capacity in vitro, in vivo, toxicological screening, body weight, motor activity, death rate, and histopathological examination of viscera. Guarana demonstrated antioxidant effects even at low concentrations by inhibiting lipid peroxidation. At high doses (1-2 g/kg IP and PO) it did not induce significant alterations in toxicological parameters. Consumption of liquids containing guarana evidenced unaltered weight of the animals even after prolonged (23 months) administration. The percentage mortality was equivalent in control and guarana groups. The absence of toxicity of guarana was also demonstrated by histopathological examination, with no alterations being detected in heart, lungs, stomach, small and large intestine, liver, pancreas, kidneys, bladder and spleen [42].
- A 10 day study in which rats were dosed at 100 mg/kg/day, approximately 50X our proposed dose in humans, demonstrated that (+)-epicatechin at this high dose demonstrated no adverse effects with respect to appetite, behavior, alertness, or appearance. No abnormalities of any organs were observed at necropsy [43].
- (+)-Epicatechin. Campos et al recently evaluated the effects of standardized Guarana encapsulated dried extract on fatigue, sleep quality, anxiety, depression symptoms, and menopause in a group of breast cancer chemotherapy patients. Patients with progressive fatigue after their first cycle of chemotherapy were randomized to receive either guarana 50 mg orally twice daily (n=32) or placebo (n=43) for 21 days. After a 7-day washout period, patients were crossed over to the opposite experimental arm. All patients were evaluated on days 1, 21, and 49. Guarana significantly improved fatigue measures vs. placebo on days 21 and 49. Guarana treatment did not produce any Common Terminology Criteria for Adverse Events grades 2, 3, or 4 toxicities and did not worsen sleep quality or cause anxiety or depression [44].

Overdose

- Neither the effects of overdose of (+)-epicatechin nor an antidote to overdose are known. For reference, the intraperitoneal (-)-epicatechin median lethal dose (LD₅₀) reported for mice is 1000 mg/kg as stated in the Material Safety Data Sheet provided by suppliers such as Sigma-Aldrich.

Pregnancy and Lactation

There are no known adverse effects of natural products containing epicatechin in pregnant women. In a developmental toxicity study in pregnant rats using a green tea extract, the no-observable-adverse-effect level (NOAEL) corresponded to 100 mg (-)-epicatechin/kg (the highest dose tested). No information is available on levels of (-)-epicatechin in breast milk.

Pregnancy testing will be done at baseline and repeated at the 12th week clinic visit. Patients who have a positive pregnancy test, are pregnant or breastfeeding will be excluded from the study.

4 Subject Selection Enrollment and Withdrawal

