ST2	Suppressor of tumorigenicity 2
TID	Ter in die (three times a day)

Study Summary

Title	A Phase II, Open Label Prospective Single Center Drug Study Evaluating the Safety and Efficacy of (+)-Epicatechin in Subjects with Friedreich’s Ataxia
Running Title	Safety and Efficacy of (+)-Epicatechin in Friedreich’s Ataxia
Protocol Number	15-006845
Phase	Phase II
Methodology	This is an open label, single center, prospective phase II drug trial to assess the safety and efficacy of (+)-EPI in the treatment of Friedreich’s Ataxia. Subjects will be evaluated at outpatient clinic visit appointments and interested qualified subjects will be consented and offered participation in this trial. Once consent has been obtained, baseline values will be established and subjects will begin treatment and follow-up over a 24 week period. Clinical and biochemical parameters will be assessed at baseline and at 12 and 24 weeks after initiation of treatment.
Overall Study Duration	Two years estimated to complete enrollment
Subject Participation Duration	24 weeks
Single or Multi-Site	Single center
Objectives	
Primary: To assess the safety and clinical efficacy from neurological, cardiac and metabolic evaluations of patients before and after treatment.
 
Secondary: To assess (i) up-regulation of relevant mitochondrial proteins (frataxin and ETC complexes I-V) and (ii) reduction of urine F2-isoprostane, before and after treatment.
 
Exploratory: To assess myocardial oxygenation by Blood Oxygenation Level Dependent (BOLD) sequence cardiac MRI, and myocardial perfusion index by Regadenoson-stress-perfusion cardiac MRI, before and after treatment as non-invasive, more sensitive endpoints for future studies.
 
To investigate neuroimaging biomarkers of disease progression including spinal cord and cerebellar volumetry, Diffusion Tensor Imaging (DTI), and Magnetic Resonance Spectroscopy (MRS).

Number of Subjects	10 subjects

Diagnosis and Main Inclusion Criteria	Study participants between the ages of ≥ 10 and ≤ 50 must have a confirmed diagnosis of Friedreich's Ataxia with disease duration ≤ 7 years and at least one affected organ system (cardiac or neurological)
Study Product, Dose, Route, Regimen	(+)-Epicatechin 25mg capsules will be administered orally TID for 24 weeks, with dose escalation to 50mg TID at 3 months for subjects not showing improvement.
Duration of Administration	24 weeks
Reference therapy	No reference therapy

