3.1 General Design

This is an open label, single center, and prospective phase II drug trial to assess the safety and efficacy of (+)-EPI in the treatment of Friedreich's ataxia. Duration of the trial including recruitment and final assessment is estimated at approximately 2 years: start date early 2016 to approximately late 2017, depending upon recruitment rate. Subjects will be evaluated at outpatient clinic visit appointments and interested qualified subjects will be consented and offered participation in this trial. Once consent has been obtained, baseline values will be established and subjects will begin treatment and follow-up over a 24 week period. Clinical and biochemical parameters shown in Table 1 will be assessed in each patient at baseline and at 3, 12 and 24 weeks after initiation of treatment. See Protocol Schedule of Events in Attachment II.

Subjects will be dispensed bottles of 25mg capsules of open-label (+) EPI with instructions for oral TID dosing to be taken on an outpatient basis. All subjects will start at 75 mg total daily dose. Those subjects showing improvement at 12 weeks as defined below, will continue at the starting dose level of 75 mg total daily dose (one, 25mg cap TID) to 24 weeks. Subjects showing no improvement or worsening at 12 weeks will have their dose escalated as described below for the remainder of the study, as tolerated.

Dose Escalation at 12 weeks: Those subjects showing no improvement or worsening in the 8 meter timed walk/FARS composite score or with no improvement in cardiac function by MRI at the 12-week clinical assessment, as compared to baseline, will have their dose increased at the 12 week visit to 150 mg total daily dose (two, 25mg caps TID) until 24 weeks, as tolerated.

Neurological Status Improvement Definition: If there is no change or the timed walk is longer at 12 weeks than at the baseline walk time or the FARs composite score has not changed or has

increased, as compared to baseline FARS composite score, this will be considered no improvement/worsening of neurological status. Improvement is defined as a greater than 1 point decrease in the FARS composite score, as compared to the baseline composite score [36].

Cardiac Status Improvement Definition: If the cardiac function is the same as baseline or worse at 12 weeks, this will be considered no improvement /worsening of cardiac LV structure/function.

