5.7 Masking/Blinding of Study

Not applicable; the study medication will be open label.

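### A primary safety endpoint compares adverse events between treatment groups, but the trial has one arm and its only groups are dose groups formed by week-12 response and tolerability

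*Combined protocol and SAP*

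**What the plan says.** Safety is part of the primary objective in both the Study Summary and Section 2. Section 3.5 (Primary Safety Endpoints) includes "Comparison between treatment groups of the incidence and types of reported adverse events including increase in migraine headaches, bruising or bleeding".

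The design has no second group:

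- The Study Summary gives, for reference therapy, "No reference therapy".
- Section 3.1: "This is an open label, single center, and prospective phase II drug trial", and "All subjects will start at 75 mg total daily dose".
- Section 5.7, on masking: "Not applicable; the study medication will be open label".

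Treatment first differs between subjects at week 12. Section 3.1: "Subjects showing no improvement or worsening at 12 weeks will have their dose escalated as described below". Those who improved stay on 75 mg/day, the others go to 150 mg/day, and the higher dose is conditional on tolerability. Section 5.2 gives the same two dose levels.

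Section 7.2 provides descriptive frequencies and percentages for categorical variables, and paired tests only (paired t, Wilcoxon signed rank, McNemar). It has no paragraph on adverse events. Section 7.3 defines one population, the protocol-compliant one. Section 4.4.1 nevertheless says that subjects withdrawn for an adverse event, by withdrawal of consent or by investigator decision will enter the safety analyses. Section 4.5 has withdrawn subjects replaced until ten complete 24 weeks, subject to capsule supply.

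**The concern.** A between-group comparison needs groups defined before, and independently of, what happens on treatment. This trial has none. An analyst who follows Section 3.5 literally must either leave the endpoint unanalysed or use the two dose groups that appear after week 12. Membership of those groups is decided by an on-treatment outcome, so a difference in migraine, bruising or bleeding between them could reflect dose, the course of the disease, or selection of subjects who tolerate the higher dose. Ten subjects cannot separate these.

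Section 3.5 is also the only place that says how adverse events will be analysed as an endpoint. If that sentence cannot be used, the denominator, the period and the measure of uncertainty for a primary objective are all left to be chosen after the data are seen.

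**Working it through.** **1. Can treatment groups be found in the documents?**

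| Candidate grouping | Source | Is it a comparison between treatment groups? |
|---|---|---|
| Active against control | Study Summary, 3.1, 5.7 | Does not exist |
| 75 against 150 mg/day, weeks 0-12 | 3.1, 5.2 | Does not exist; all subjects take 75 mg/day |
| 75 against 150 mg/day, weeks 12-24 | 3.1, 5.2 | Exists, but is formed by week-12 response and tolerability |
| Weeks 0-12 against weeks 12-24 in the same subjects | 3.1 | Not between groups; mixes any dose effect with time on drug |

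Only the third row gives two groups, and assignment to them is not independent of outcome. Adverse events from the first half of follow-up cannot enter that comparison.

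**2. Does the plan's sample size support a group comparison?** Section 7.1 states 80% power with n = 10 and effect size 1, using a paired t-test at 5% (two-sided, per Section 7). Check by the noncentral t distribution:

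- degrees of freedom = 10 - 1 = 9
- noncentrality = 1 × √10 = 3.162
- power = P(|T| > t₀.₉₇₅,₉) = 0.803

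The stated 80% reproduces. It applies to a within-subject change in one cohort and says nothing about a contrast between subgroups of the ten.

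**3. What can one-arm reporting deliver?** Exact (Clopper-Pearson) 95% limits for x subjects with an event out of n = 10:

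- x = 0: lower 0; upper = 1 - 0.025^(1/10) = 0.3085. Interval 0% to 31%.
- x = 1: lower = 1 - 0.975^(1/10) = 0.0025; upper solves (1-p)^10 + 10p(1-p)^9 = 0.025, giving p = 0.445. Interval 0.3% to 45%.
- x = 2: by the same method, 2.5% to 55.6%.

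The chance that at least one of ten subjects has an event with true rate p is 1 - (1-p)^10. The documents give no event rates, so p is an assumption:

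- p = 5%: 1 - 0.95^10 = 40%
- p = 10%: 1 - 0.90^10 = 65%
- p = 20%: 1 - 0.80^10 = 89%

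**4. Denominator.** Because withdrawn subjects are replaced, the number treated may exceed ten. If two were replaced (an assumption), 0/12 would give an upper limit of 1 - 0.025^(1/12) = 0.265. An analysis limited to the protocol-compliant population would leave out subjects that Section 4.4.1 says must be counted.

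**The case against.** The best defence is that this is carried-over template wording. Section 8.3.2 mentions a placebo that the trial also lacks. Any sensible analyst of an open-label study without a comparator would report single-arm incidence. The data for that will exist: Section 8.2 records all adverse events, Section 7.2 provides for frequencies and percentages, and Section 4.4.1 keeps withdrawn subjects in. The study-level safety decisions in Sections 8.4 and 8.5 rest on the number and type of serious events and on deaths, not on a group comparison. All of this stands. It means that subject protection does not depend on the endpoint. It does not make a primary endpoint workable as written, and it does not fix a denominator or interval in advance.

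A reader might infer more than the documents support, in four ways:

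- **That the dose groups differ in time on drug.** They do not, apart from early withdrawals. Both have about 12 weeks at 75 mg/day and then run in parallel to week 24. Time becomes a confounder only if 75 mg experience from weeks 0-12 is pooled into the comparison.
- **That the higher dose goes to sicker subjects.** Selection by response is clear; its direction is not. Unchanged subjects also escalate. Each cardiac improvement criterion in Section 3.1 requires an abnormal baseline value, so a subject with normal values cannot meet any of them and, on one reading of the escalation rule, would escalate. The visit description in Section 3 words that rule differently, and the two need to be reconciled.
- **That no safety result would be produced.** Incidence could still be reported, for the reasons above.
- **That the problem is an underpowered test.** With an assumed 5/5 split, a two-sided Fisher test first reaches 0.05 at 4/5 against 0/5 (p = 2 × 5/210 = 0.048) or its mirror, 5/5 against 1/5. But the plan names no such test and gives no split. Confounding, not power, is the reason to drop the comparison.

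**Conclusion.** The point holds. Section 3.5 asks for a comparison that a one-arm trial cannot supply. The only available substitute, 75 against 150 mg/day in weeks 12-24, confounds dose with week-12 response and tolerability and cannot use events from weeks 0-12. Nothing in Section 7 repairs this, and Section 7.3 lacks the safety population that Section 4.4.1 presupposes.

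This rests on the design text alone and needs no assumed rate or split. What the trial can offer is single-arm incidence with wide limits: an upper limit of about 31% when no event is seen in ten subjects, and about 45% when one is seen. Those widths follow from n = 10 under any wording; they show what can honestly be claimed. The wording should be corrected before analysis. It does not affect the stopping rules.

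**What to change.** 1. **Section 3.5.** Replace the between-group comparison with the number and percent of subjects with each adverse event, naming migraine, bruising, bleeding and hypotension (the last is already discussed there as a potential risk), among all subjects who received any dose, with exact 95% confidence intervals.
2. **Section 7.2.** Add a short safety paragraph. Tabulate events descriptively by period (weeks 0-12 and weeks 12-24, divided at each subject's actual week-12 visit) and, within weeks 12-24 only, by dose at onset. Make no test between doses, and state that the dose groups are formed by response and tolerability. The split by period is needed because a table by dose at onset alone would place every early event at 75 mg and so mix dose with time.
3. **Section 7.3.** Add a safety population of all subjects who received any study drug, including withdrawn subjects and those later replaced, consistent with Section 4.4.1. Say explicitly that subjects dropped for non-compliance under Section 5.4 are included, since Section 4.4.1 does not mention them.

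The cost is the revised endpoint sentence plus a short paragraph on safety population and analysis. It needs no new data, visits or subjects, and changes no dose or clinical rule.

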4.1 Inclusion Criteria

Subjects must fulfill all of the following criteria:

Inclusion criteria:

- Confirmed diagnosis of Friedreich's ataxia by *FXN* genetic testing and/or Frataxin enzyme analysis
- Between age 10 and 50 years of age, inclusive
- Body weight of 25 kg or higher
- Minimum of one affected organ (cardiac or neurological) system, as evidenced by clinical signs/symptoms
- Disease duration ≤ 7 years, based on onset date of FA symptoms
- Has no known contraindication to gadolinium contrast such as severe allergy or GFR < 30 ml/min/m².
- Has no known contraindication to non-contrast MRI evaluation such as pacemaker or magnetically active metal fragments.
- Women of childbearing age must:
 - Have a negative pregnancy human chorionic gonadotropin test prior to receiving study drug.
 - Agree to use contraception for the duration of the study drug dosing, plus 1 month after completion of the study.

4.2 Exclusion Criteria

Exclusion criteria:

- Advanced cardiac failure, NYHA Class IV.

- Clinically significant comorbidities that may also lead to cardiomyopathy, for example long standing hypertension, familial cardiomyopathy.
- Clinically significant comorbidities that would, in the opinion of the investigators, compromise the interpretation of test results.
- Pregnant, breast-feeding or planning to become pregnant during study timeframe.
- Patients with contraindications to regadenoson, i. e. second- or third-degree atrioventricular (AV) block or sinus node dysfunction. Has received an investigational drug within thirty (30) days of baseline visit.
- Thrombocytopenia ($<125 \times 10^9/L$) or prolonged PT/PTT at baseline.
- Clinically significant hypotension (systolic BP <90) due to heart failure or other conditions.

4.3 Subject Recruitment, Enrollment and Screening

Subjects may be recruited:

- From the Principal Investigator or Sub-Investigator's clinical practices; may also be identified by Study Coordinator.
- By physician referrals within Mayo Clinic, by referrals from non-Mayo Clinic physicians, by contact made via the Mayo Clinical Trials database with a link to the national ataxia foundation web site, or by patient inquiries via contacts listed on the www.clinicaltrials.gov registry.
- Mayo Clinic investigators using social media (e.g. Twitter, Facebook, YouTube, etc.) as a recruitment method must have the research reviewed and approved by the Mayo Clinic Public Affairs/Center for Social Media.
- New projects proposing the use of social media as a recruitment method will contain a statement from the PI in the IRBe application or the research project proposal that the use of social media for recruitment of research subjects has been reviewed and approved by the Mayo Clinic Public Affairs/Center for Social Media.
- Investigators at institutions for which the Mayo Clinic IRB is the IRB of record will include within the IRB application documentation of review and approval by the relying organization for the use of social media, or documentation that such review and approval is not required by the institution.

Enrollment

Study participants with genetically confirmed diagnosis of FA who meet inclusion criteria and do not meet exclusion criteria will be enrolled according to the most current IRB approved version of this protocol. Adequate time will be allowed for review of consent/assent and to ask questions about the study prior to enrollment. Subjects aged 13-17 will also sign an IRB approved assent. A copy of the signed consent/assent form will be provided to the subject/LAR and the original will be retained in the Investigator's study file. A copy of the signed forms will also be scanned into the subject's Mayo Clinic electronic medical record.

Documentation of informed consent/HIPAA authorization will involve the use of the Research Participant Tracking (PTrax) Digital Signature Capture technology for research informed consent forms/HIPAA authorization forms. This is an institutionally approved process for obtaining

consent/HIPAA authorization only while the subject, and/or the subject's representative, is in the physical presence of the person authorized to obtain consent. The study team may print a copy of the signed consent form/HIPAA authorization form for the subject or their representative. The consent form/HIPAA authorization form will also be available to the subject via the patient portal. **Note:** If the subject or their representative prefers not to use the Digital Signature Capture technology, the study team will provide a paper consent form/HIPAA authorization form for signature.

